6.7 BASELINE, TIME WINDOWS AND CALCULATED VISITS

For an overview on planned visits refer to Flow Chart in the CTP.

As a general rule, last assessment before first trial drug intake (included) will be used as baseline. If the baseline value is missing and the screening value is available, then the baseline value will be defined as the screening value taken closest to baseline date.

A windowing will be performed as described in [Tables 6.7: 1](#) and [6.7: 2](#), in order to assign data to the relevant study visit based on the actual day of the assessment. Data will be analyzed using the re-calculated visits in the statistical tables. However, in the listings, all visits performed will be displayed (even if outside time-window), along with the re-calculated visit.

If after windowing of visits at baseline, two values fall within the same baseline interval, then the last value will be taken into account. If after windowing of post-baseline visits, two visits fall in the same interval, then the measurement closest to the planned visit will be taken into account. In case two measurements are equidistant from the planned visit, then the last one will be picked. The same rules will be applied for laboratory measurements.

If after windowing of post-baseline visits, two values fall within the same interval “Follow-up”, then only the first value will be taken into account.

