4.2.1.3 Recommendations for management of liver enzyme elevation

For a detailed guidance on how to manage liver enzyme elevations, please refer to [table 4.2.1.3: 1](#)

Table 4.2.1.3: 1 Recommendations for managing liver enzyme elevations

AST /ALT $\geq 3$ but $< 5$ x ULN		AST /ALT $\geq 5$ but $< 8$ x ULN		Signs of hepatic injury 
Reduce study medication to 100 mg bid or interrupt (at the discretion of the investigator) Repeat Lab tests  in 48/72 hours, at week 1 and week 2		Interrupt study medication Repeat Lab tests  in 48/72 hours, at week 1 and week 2		Permanently discontinue study medication
If AST /ALT $< 3$ x ULN within 2 weeks	If AST /ALT $\geq 3$ ULN at 2 weeks	If AST /ALT $< 3$ x ULN within 2 weeks	If AST /ALT $\geq 3$ ULN at 2 weeks	
Re-escalate study medication to 150 mg bid if reduced; restart at 100 mg bid if interrupted Repeat Lab tests  in 2 and 4 weeks	Interrupt study medication Repeat Lab tests  in 1 and 2 weeks	Reintroduce study medication at 100 mg bid Lab tests  in 1, 2 and 4 weeks	Permanently discontinue study medication	
If AST / ALT $\geq 3$ x ULN within 2 weeks	If at 2 weeks	If AST / ALT $\geq 3$ x ULN within 2 weeks		
Permanently discontinue study medication	AST / ALT $< 3$ x ULN reintroduce study medication; lab tests  every week as needed  If AST / ALT $\geq 3$ x ULN permanently discontinue study medication	Permanently discontinue study medication		

Laboratory tests include ALT, AST, total bilirubin, eosinophils, INR

 Signs of hepatic injury are defined as:

- ALT and/or AST  $\geq$  8 fold ULN
- ALT and/or AST  $\geq$  3 fold ULN and total bilirubin  $\geq$  2 fold ULN
- ALT and/or AST  $\geq$  3 fold ULN and unexplained INR  $>$  1.5
- ALT and/or AST  $\geq$  3 fold ULN and unexplained eosinophilia ( $>$  5%)
- ALT and/or AST  $\geq$  3 fold ULN and appearance of fatigue, nausea, vomiting, right upper abdominal quadrant pain or tenderness, fever and/or rash.

For potential drug induced liver injury (DILI) follow up requirements please see [Section 5.3.6.1](#).

Immediately refer to [Section 5.3.6.1](#) in case AST and/or ALT  $\geq$ 3 fold ULN is combined with total bilirubin  $\geq$ 2 fold ULN.

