 - last trial drug intake plus 29 days
 - date of trial completion
 - follow-up visit
 - early end of treatment visit plus 1 day to database lock

^[a] In addition, a post-treatment period of 7 days will be used for adverse event analyses to more closely reflect the period of time after the last trial drug intake when measurable drug levels or pharmacodynamic effects are still likely to be present.

In addition to the above periods, the following additional period is defined:

- Overall: Combines all available data from Blinded treatment period and Open-label treatment period.

For safety analyses, data up to the end of the blinded / open-label post-treatment period will be considered on-treatment. For on-treatment efficacy analyses, data up to the day after last trial drug intake (included) will be considered.

For efficacy analyses patients will be assigned to the treatment group they were randomised to, for safety analyses patients will be assigned to the treatment group they were treated in.

Details are provided in [Table 6.1: 1](#).

Table 6.1: 1 Summary of analysed periods according to the type of endpoint

Analysed endpoint	Studied period	
	Start date	End date ^{1/1}
For primary analysis (rate of change (slope) in blood CRPM from baseline to week 12)	Baseline (see Section 6.7)	Visit 5 (after time windowing, refer to Section 6.7) Data up to the day after last blinded trial drug intake (included).
For the key secondary endpoint (Proportion of patients with disease progression as defined by absolute FVC (% predicted) decline $\geq 10\%$ or death until week 52)	Main analysis: Baseline (see Section 6.7) Sensitivity analysis: Visit 5 (start of open label treatment)	Visit 10 (after time windowing, refer to Section 6.7) Data up to the day after last open-label trial drug intake (included).
For secondary endpoints (rate of change (slope) in blood C1M and C3M from baseline to week 12)	Baseline (see Section 6.7)	Visit 5 (after time windowing, refer to Section 6.7) Data up to the day after last blinded trial drug intake (included).
For efficacy endpoints from week 12 to week 52 (open-label period)	Visit 5 (start of open label treatment) Note: Covariates can be measured before Visit 5.	Visit 10 (after time windowing, refer to Section 6.7) Data up to the day after last trial open-label drug intake (included).

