7.8.2 Laboratory data

The analyses of laboratory data will be descriptive in nature and will be based on BI standards (see DM&SM: Display and Analysis of Laboratory Data) ([12](#)).

Please refer to Section 7.3.4 of the CTP. Please refer to [Section 5.4.4](#) for a definition of liver enzyme elevations.

Specific tables will be presented to describe liver enzyme elevations as defined in Section 5.4.4 by treatment group:

- Summary table of liver enzyme elevation including time to first onset and number of patients with liver enzyme elevation.
- Kaplan-Meier plot of time to first liver enzyme elevation (if sufficient number of events). No statistical test will be performed.
- Summary table of individual maximum liver enzyme and bilirubin elevations
- Plot of time course profile of liver enzyme for patients having liver enzyme and bilirubin elevation

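### Read literally, the one-value-per-window rule in SAP 6.7 can drop off-schedule liver values from the maximum, patient-count and time-to-first-elevation outputs in SAP 7.8.2

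*SAP*

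**What the plan says.** SAP 6.7 assigns each assessment to a visit by its actual day. It then states: "Data will be analyzed using the re-calculated visits in the statistical tables". If post-baseline visits share a window, "two visits fall in the same interval, then the measurement closest to the planned visit will be taken into account". Ties are settled by date: "In case two measurements are equidistant from the planned visit, then the last one will be picked". In the Follow-up interval only the first value is used. The section extends all this to laboratory data: "The same rules will be applied for laboratory measurements". Listings are treated differently: "in the listings, all visits performed will be displayed (even if outside time-window), along with the re-calculated visit".

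SAP 7.8.2 plans a "Summary table of individual maximum liver enzyme and bilirubin elevations", a summary of time to first onset and number of patients with an elevation, and a Kaplan-Meier plot of time to first elevation. It refers to SAP 5.4.4 for the definition of an elevation.

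Protocol Table 4.2.1.3:1 asks for repeat liver tests "in 48/72 hours, at week 1 and week 2" once AST or ALT reaches 3 times the upper limit of normal (ULN) without signs of hepatic injury.

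SAP Table 6.1:1 sets the periods for laboratory data and enzyme elevations by date of drug intake. One row pairs a bilirubin rise with an AST or ALT rise within 30 days.

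**The concern.** Keeping the value nearest the planned day is sensible for a by-visit mean or a repeated-measures model. It does not suit a maximum, a threshold count or a time to first event, because it selects on closeness to schedule and ignores the value itself. The protocol deliberately creates off-schedule liver samples in the patients whose enzymes are raised, and those samples show whether the elevation is progressing. The visible text of 6.7 and 7.8.2 makes no exception for these outputs.

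Liver enzyme elevation is a named risk of nintedanib (Protocol 1.2 and 2.3), and hepatic injury is an adverse event of special interest (Protocol 5.3.6.1). Tables that miss the peak or the first raised value would describe that risk as milder or later than the data show.

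**Working it through.** No figure stated in the plan is in dispute on this point, so the check is of what the rule does.

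**Inputs.** Selection and tie rules: SAP 6.7. Outputs: SAP 7.8.2. Repeat tests at 2 to 3, 7 and 14 days: Protocol Table 4.2.1.3:1. Planned visits at weeks 4, 8, 12, 16, 20, 24, 36 and 52: Protocol 6.1. Assumption: windows are cut at midpoints between planned visits, because the window tables are not public.

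**1. When a repeat is dropped.** Let a scheduled sample be taken e days from its planned day (negative if early) and a repeat k days later in the same window. The repeat is dropped when |e| < |e + k|.
- If e ≥ 0, this holds for every k > 0.
- If e < 0, the repeat wins when k ≤ 2|e|; a tie goes to the later value. With e = −3, repeats at k = 2 and k = 3 lie 1 and 0 days from plan and beat the visit value. A repeat at k = 7 lies 4 days from plan and does not.

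**2. Do repeats share the window?** Half the gap between visits is 28/2 = 14 days up to week 24, 84/2 = 42 days between weeks 24 and 36, and 112/2 = 56 days between weeks 36 and 52. Repeats 2, 3, 7 and 14 days after an on-schedule visit at weeks 4 to 36 therefore stay in that visit's window. Day 14 is exactly the boundary where the gap is 4 weeks.

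**3. Effect on each output (invented values).**
- Maximum: the week-12 visit is on day 12 × 7 + 1 = 85 with ALT 3.5 times ULN; the repeat on day 88 shows ALT 6 times and bilirubin 2.2 times ULN. Distances are 0 and 3 days, so day 85 is kept and the maximum is tabulated as 3.5. Time to first value of at least 3 times ULN is day 85 either way.
- Time to first: move that visit to day 82 and the repeat to day 85. The repeat is kept, the maximum of 6 is right, and onset moves from day 82 to day 85.
- Number of patients: an unscheduled elevation at week 32 falls in the week-36 window, because the midpoint of weeks 24 and 36 is week 30. If the week-36 value is on schedule and normal, it is kept, and a patient with no other elevation is counted as having none.

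**4. How readily the rule applies.** Suppose an unscheduled sample falls on a uniformly random day from 1 to 371, scheduled visits fall uniformly within ±j days of plan, and a fraction m of visits is missed. Days 1 to 371 split into 16 half-windows totalling 370 days. Within each, the expected length over which the unscheduled sample is the closer one is j/2. The share dropped is therefore (1 − m)(1 − 16 × (j/2)/370) = (1 − m)(1 − 8j/370).
- j = 3, m = 0: 1 − 24/370 = 0.935.
- j = 7, m = 0.20: 0.80 × (1 − 56/370) = 0.679.

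A simulation of the same set-up gave 0.936 and 0.678. This is the share of unscheduled samples that lose to a scheduled one. It is not the share of qualifying liver values lost, for which the documents give no rate.

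**5. Against Table 6.1:1.** The efficacy rows carry windowing language, for example "Visit 10 (after time windowing, refer to Section 6.7". The laboratory and liver rows do not: they run by date from first intake, do not exclude interruptions, and use a 30-day pairing that only makes sense with actual sample dates. These rows say which dates are in scope. They do not say which value is kept when two fall in one window, and on that the only visible rule is 6.7.

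**The case against.** The strongest reply is that windowing serves by-visit displays and was never meant for maxima or event times. Table 6.1:1 supports this through its date-based liver rows and 30-day pairing. The places where an all-values rule would normally sit are not public: SAP 5.4.4, the window tables, and the sponsor's standard for laboratory data cited in 7.8.2. The safety signal also has other routes: 24-hour reporting of hepatic injury, separate adverse event groupings for enzyme and bilirubin increases, and listings that show every visit. All laboratory analyses are descriptive.

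Most of this stands as a limit on certainty and size. It does not remove the point. If all samples are intended, the unqualified sentence on laboratory measurements in 6.7 says otherwise and needs correcting. Complete listings do not repair a wrong maximum or a wrong Kaplan-Meier plot.

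A reader might go further and infer that ordered repeats are always discarded. They are not: a repeat after an early visit can be the value kept, and a value alone in its window is kept.

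A reader might also infer that the key secondary endpoint loses FVC progression events, since Table 6.1:1 ends it at Visit 10 after windowing. The documents give little support for that. The same row stops data at the day after last intake, which already removes most early end-of-treatment spirometry (Protocol 6.2.3). SAP 6.6 imputes missing binary outcomes as worst case. Unscheduled visits are allowed, but no visible visit description plans off-schedule clinic spirometry. The stated 88% power reproduces: with 233/2 = 116.5 per group, (0.20 × √116.5 − 1.96 × √0.48)/√0.46 = 1.18, which gives 0.881. Nothing here shows it to be wrong.

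**Conclusion.** The point holds in a limited form. SAP 6.7, as visibly written, applies a by-visit selection rule to all laboratory data in the statistical tables. Followed literally, it can remove the peak or first liver value from the 7.8.2 outputs. That is a stated rule giving a wrong result for these outputs, which is more than a missing detail.

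Leaving values out can only lower maxima, reduce the number of patients with an elevation, or delay onset. The loss is conditional: another value in the same window must lie closer to plan. Its size cannot be estimated from the documents, and the examples above rest on assumed midpoint windows and invented laboratory values. An exemption in SAP 5.4.4 cannot be ruled out. The key secondary endpoint needs at most a clarifying sentence.

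**What to change.** In SAP 6.7, limit the closest-value and first-Follow-up-value rules to by-visit summaries and visit-based models. In SAP 7.8.2, state that the maximum, threshold and time-to-first liver outputs use all values, scheduled and unscheduled, by actual date within the on-treatment period of Table 6.1:1. If SAP 5.4.4 already says this, a cross-reference in 6.7 is enough. For FVC progression, one sentence can confirm that every valid supervised clinic value within the existing cut-off counts.

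The cost is a few sentences and a programming flag. No new data are needed, since the listings already draw on all visits. The one visible consequence is that slightly more elevations may be reported.

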7. PLANNED ANALYSIS

For End of Text tables, the set of summary statistics is: N / Mean / SD / Min / Median / Max ([7](#)).

Tabulations of frequencies for categorical data will include all possible categories and will display the number of observations in a category as well as the percentage (%) relative to the respective treatment group (unless otherwise specified, all patients in the respective patient set whether they have non-missing values or not). Percentages will be rounded to one decimal place. The category missing will be displayed only if there are actually missing values.

7.3 TREATMENT COMPLIANCE

Only descriptive statistics are planned for this section of the report.

7.4 PRIMARY ENDPOINT

7.4.1 Primary analysis

Please refer to Section 7.3.1 of the CTP.

The primary analysis will be done on the TS.

All visits from baseline to week 12 will be included in the primary analysis, after time-windowing. Measurements after week 12 (after time windowing) are not taken into consideration for this endpoint.

Refer to [Section 9.1](#) for SAS code specifications.

Efficacy evaluations done after lung transplant will not be used for the efficacy analyses.

7.5 SECONDARY ENDPOINT(S)

7.5.1 Key secondary endpoint(s)

The key secondary endpoint is defined as the proportion of patients with disease progression as defined by absolute FVC (% predicted) decline $\geq 10\%$ or death until week 52.

The following analyses are planned:

- Firstly, in order to assess the association of change in extracellular matrix (ECM) biomarker CRPM over 12 weeks with disease progression as defined by FVC decline $\geq 10\%$ or death over 52 weeks, a logistic regression analysis including baseline blood

CRPM and the rate of change (slope) in blood CRPM over the first 12 weeks as covariates will be applied **for the placebo treated patients only**.

By doing this, the potential of CRPM as a prognostic biomarker is evaluated.

- Secondly, in order to assess how Nintedanib treatment during the first 12 weeks affects the association between change in extracellular matrix (ECM) biomarker CRPM over 12 weeks and disease progression, a logistic regression analysis including baseline blood CRPM, rate of change (slope) in blood CRPM over the first 12 weeks, treatment and treatment CRPM slope interaction as covariates will be applied. **The interaction term will be of primary interest within this analysis.**
- Thirdly, in order to assess whether the overall treatment regimen affects disease progression as defined by FVC decline $\geq 10\%$ or death over 52 weeks, a logistic regression analysis including baseline blood CRPM and randomized treatment as covariates will be applied. **The treatment effect will be of primary interest within this analysis.**
- Fourthly, in order to assess whether rate of change (slope) in blood CRPM over the first 12 weeks to some extent explains the effect of treatment regimen on disease progression as defined by FVC decline $\geq 10\%$ or death over 52 weeks, a logistic regression analysis including baseline blood CRPM, rate of change (slope) in blood CRPM over the first 12 weeks and randomized treatment as covariates will be applied. **The treatment effect will be of primary interest within this analysis.**

Patients who died or progressed in the blinded phase are not at risk in the open label period, but will be considered in the main analysis (including their progression and/or death).

The four main analyses of the key secondary endpoint outlined at the beginning of this section will be repeated by replacing CRPM by C1M and C3M, respectively.

7.5.2 Other Secondary endpoints

The following secondary endpoints are defined:

- Rate of change (slope) in blood C1M from baseline to week 12
- Rate of change (slope) in blood C3M from baseline to week 12

Please refer to Section 7.3.2 of the CTP for further details of the analysis.

This endpoint will be analyzed in a similar manner as the primary endpoint. Reasonably, baseline CRPM as covariate will be replaced by baseline C1M and C3M in these analyses.

7.8 SAFETY ANALYSIS

All safety analyses will be performed on the TS.

7.8.1 Adverse events

Unless otherwise specified, analyses of adverse events will be descriptive in nature and will be based on BI standards ([10](#)). No hypothesis testing is planned. All analyses of AEs will be based on the number of patients with AEs and NOT on the number of AEs.

Furthermore, for analysis of AE attributes such as duration, severity, etc. multiple AE occurrence data on the CRF, will be collapsed into AE episodes provided that all of the following applies:

- The same MedDRA lowest level term was reported for the occurrences
- The occurrences were time-overlapping or time-adjacent (time-adjacency of 2 occurrences is given if the second occurrence started on the same day or on the day after the end of the first occurrence)
- Treatment did not change between the onset of the occurrences OR treatment changed between the onset of the occurrences, but no deterioration was observed for the later occurrence

For further details on summarization of AE data, please refer to the guideline “Analysis and Presentation of Adverse Event Data from Clinical Trials” ([10](#)).

The analysis of adverse events will be based on the concept of treatment emergent adverse events. That means that all adverse events occurring between first drug intake till 28 days after last drug intake (end of the residual effect period) will be assigned to the randomised treatment. Note that analysis of adverse events will be repeated considering only data until 7 days after last drug intake as treatment emergent (see also [Section 6.1](#)). Adverse events that start before first drug intake and deteriorate under treatment will also be considered as ‘treatment-emergent’.

All adverse events occurring before first drug intake and do not deteriorate under treatment will be assigned to ‘screening’ or ‘post-randomisation’ and all adverse events occurring after last drug intake will be assigned to ‘residual effect period’, ‘post-study’ or ‘follow-up’ (for listings only). Also, all AEs occurring between the start of an interruption and the end of interruption will be assigned to ‘off-treatment’ period in the listings. For details on the treatment definition, see Section 6.1.

According to ICH E3 ([11](#)), AEs classified as ‘other significant’ will include those non-serious and non-significant adverse events with

- (i) ‘action taken = discontinuation’ or ‘action taken = reduced’, or
- (ii) marked haematological and other lab abnormalities or lead to significant concomitant therapy as identified by the Clinical Monitor/Investigator at a Blinded Report Planning Meeting.

An overall summary of adverse events will be presented. The frequency of patients with adverse events will be summarized by treatment, primary system organ class and preferred term. Separate tables will be provided for patients with other significant adverse events according to ICH E3 (11), for patients with adverse events occurring with an incidence in preferred term greater than 5% (in at least one treatment arm), for patients with adverse events leading to dose reduction, for patients with adverse events leading to treatment discontinuation, for patients with serious adverse events, for patients with related adverse events and for patient with significant (protocol-specified) AEs (as ticked in the AE page of the CRF).

The system organ classes will be sorted according to the standard sort order specified by EMA, preferred terms will be sorted by frequency (within system organ class).

Specific tables will be created in order to describe diarrhoea events:

- Display of the diarrhoea specific page of the CRF
- Summary of diarrhoea events including time to onset, number and duration of episodes

- Summary of diarrhoea adverse events including seriousness, clinical consequences (dose reduction, drug discontinuation or drug interruption) and outcome

Also, a Kaplan-Meier plot of time to first diarrhoea event will be drawn by treatment.

Similar summary tables including seriousness, clinical consequences and outcome will also be presented to describe the bleeding adverse events. Depending on the number of patients having such adverse events, summary tables including time to onset, number of episodes and duration together with Kaplan-Meier plot of time to first event may also be produced.

The following adverse event groupings have been defined outside the trial protocol:

Table 7.8.1: 1 Adverse events by system using aggregated terms

System	Safety Topic	Definition (selection criteria)
Gastrointestinal	Diarrhoea	PT Diarrhoea
	Nausea	PT Nausea
	Abdominal pain	HLT 'Gastrointestinal and abdominal pains (excl oral and throat)
	Vomiting	PT Vomiting
	Pancreatitis	SMQ Acute pancreatitis (narrow)
	Gastrointestinal perforation	SMQ Gastrointestinal perforation (narrow)
	Hepatobiliary	Drug-induced liver injury (DILI)
Hepatic disorders (broad)		Table to show cumulative row for all 4 SMQs below, followed by a cumulative row for each subSMQ, followed by all PTs driving that subSMQ
Drug related hepatic disorders		SMQ Drug related hepatic disorders – comprehensive search (narrow) OR
Liver related investigations		SMQ Liver related investigations, signs and symptoms (broad) OR
Cholestasis and jaundice of hepatic origin		SMQ Cholestasis and jaundice of hepatic origin (narrow) OR
	Hepatitis non-infectious	SMQ Hepatitis, non-infectious (narrow)
	Hepatic failure	SMQ Hepatic failure, fibrosis and cirrhosis and other liver damage-related conditions (narrow)
Cardiovascular	Arterial thromboembolism	SMQ Embolic and thrombotic events, arterial (narrow)
	Myocardial infarction	SMQ Myocardial infarction (narrow)
	Stroke	PV Endpoint, see Section 9.2 for included Preferred Terms

Table 7.8.1: 1 (continued) Adverse events by system using aggregated terms

System	Safety Topic	Definition (selection criteria)
	MACE	Fatal events in SOC Cardiac Fatal events in SOC Vascular Any fatal or nonfatal events in SMQ Myocardial infarction (narrow) PTs Cardiac death, Sudden death, Sudden Cardiac death Any fatal or nonfatal Stroke events as defined in respective PV Endpoint
	Cardiac failure	SMQ Cardiac failure (narrow)
	QT prolongation	SMQ Torsade de pointes/QT prolongation (narrow)
	Venous thromboembolism	SMQ Embolic and thrombotic events, venous (narrow)
	Pulmonary embolism	PT Pulmonary embolism
	DVT	PT Deep vein thrombosis
	Hypertension	SMQ Hypertension (narrow)
Metabolic	Decreased appetite	PT Decreased appetite
	Weight decreased	PTs: Weight decreased, Abnormal loss of weight
Blood	Thrombocytopenia	PTs: Thrombocytopenia, Platelet count decreased, Immune thrombocytopenic purpura
	Haematopoietic thrombocytopenia	SMQ Haematopoietic thrombocytopenia (broad)
	Neutropenia	SMQ Agranulocytosis (narrow) OR SMQ Haematopoietic leukopenia (narrow)
	Bleeding	SMQ Haemorrhage terms (excl laboratory terms) (narrow) displayed in total and then according to categories: 
 • Gastrointestinal – oral • Gastrointestinal – upper • Gastrointestinal – lower • Gastrointestinal – nonspecific • Skin • Respiratory • CNS • Urogenital • Other
	GI bleeding – oral	
	GI bleeding – upper	
	GI bleeding – lower	
	GI bleeding – nonspecific	
	Skin bleeding	
	Respiratory bleeding	
	CNS bleeding	
	Urogenital bleeding	
	Other bleeding	
		See Section 9.3 for PT lists of the bleeding subcategories.
Psychiatric	Depression	SMQ Depression (excl suicide and self-injury) (narrow)
	Suicide	SMQ Suicide/self-injury (narrow)
Renal	Renal failure	SMQ Acute renal failure (narrow)
	Proteinuria	SMQ Proteinuria (narrow)
	Glomerulonephritis	SMQ Chronic kidney disease (broad)
Cutaneous	Severe skin reactions	SMQ Severe cutaneous adverse reactions (narrow)
	Pruritus	PT Pruritus
	Rash	BIcMQ subsearch “Skin rash” (narrow)

Table 7.8.1: 1 (continued) Adverse events by system using aggregated terms

System	Safety Topic	Definition (selection criteria)
Liver laboratories	Hepatic enzyme increased	Following PTs: Alanine aminotransferase abnormal Alanine aminotransferase increased Aspartate aminotransferase abnormal Aspartate aminotransferase increased Hepatic enzyme abnormal Hepatic enzyme increased Hepatic function abnormal Hypertransaminasaemia Liver function test abnormal Transaminases abnormal Transaminases increased Blood alkaline phosphatase abnormal Blood alkaline phosphatase increased Gamma-glutamyltransferase abnormal Gamma-glutamyltransferase increased
	Hyperbilirubinaemia	Following PTs: Blood bilirubin abnormal Blood bilirubin increased Blood bilirubin unconjugated increased Hyperbilirubinaemia Icterus index increased Jaundice Jaundice hepatocellular Bilirubin conjugated abnormal Bilirubin conjugated increased
	Alanine aminotransferase increased	Following PTs: Alanine aminotransferase increased Alanine aminotransferase abnormal
	Aspartate aminotransferase increased	Following PTs: Aspartate aminotransferase increased Aspartate aminotransferase abnormal
	Gamma-glutamyl-transferase increased	Following PTs: Gamma-glutamyltransferase increased Gamma-glutamyltransferase abnormal
	Blood alkaline phosphatase increased	Following PTs: Blood alkaline phosphatase increased Blood alkaline phosphatase abnormal

These definitions are based on MedDRA version 21.0.

For analyses defined above, the blinded and open-label period will be analyzed separately. Additionally, a pooled analysis across both periods will be performed but including displays by randomized treatment.

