#### **Randomised Set (RS):**

The Randomised set (RS), consists of those patients who were randomised to a treatment group.

The efficacy and safety analysis will be conducted on the TS. Efficacy parameters will be analysed from an as randomised perspective and safety parameters from an as treated perspective, respectively. For efficacy analysis, all measurement performed within the first 12 weeks will be used. Efficacy evaluations done after lung transplant will not be used for the efficacy analyses; sensitivity analyses will be performed including these data.

Although there is no per protocol data set in the study, reasons for important protocol violations will be specified in the Trial Statistical Analysis Plan (TSAP). Patients with potential important protocol violations (those that relate to patient safety or efficacy) will be identified at Blinded Review Planning Meetings and listed in the clinical trial report.

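### SAP 7.8.1 attributes treatment-emergent adverse events to the randomised treatment, against the as-treated safety rule in SAP 6.1 and protocol 7.3; separately, the pooled display by randomised arm mixes placebo and nintedanib time without a required sequence label

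*SAP*

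**What the plan says.** **Attribution rule.** SAP 7.8.1 defines treatment-emergent events as those from first drug intake to 28 days after last drug intake, and says that they "will be assigned to the randomised treatment". The sentence makes no cut at the switch to open label and no exception for patients who took the wrong drug.

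**As-treated rule.** SAP 6.1 says that "for safety analyses patients will be assigned to the treatment group they were treated in". Protocol 7.3, in the text under the Randomised Set, says: "Efficacy parameters will be analysed from an as randomised perspective and safety parameters from an as treated perspective, respectively". SAP section 4, on changes to the planned analysis, is marked not applicable.

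**Displays.** SAP 7.8.1 closes by saying that "the blinded and open-label period will be analyzed separately" and then that "a pooled analysis across both periods will be performed but including displays by randomized treatment".

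**Period boundaries.** SAP 6.1 and Table 6.1: 1 end the blinded on-treatment safety period at first open-label intake, at 28 days after last blinded intake, or at end of treatment, whichever comes first. The overall period runs across both.

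**Design.** Protocol 3.1 gives 12 blinded weeks and 40 open-label weeks, and moves all placebo patients to nintedanib at the end of the first part.

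**The concern.** Two sentences in the same SAP give different answers to one programming question: which treatment an adverse event is counted under. For a patient who takes only what was randomised, during the blinded period, the answers agree. They part in two situations.

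- **Medication errors.** Codes C1 and C2 in Table 6.2: 1 provide for patients whose wrong kit leads to an actual treatment switch, and exclude none of them from any analysis set. Under SAP 6.1 the events of such a patient follow the drug received. Under the 7.8.1 sentence they stay with the randomised arm.
- **The planned switch at week 12.** A 52-week display grouped by randomised arm is a comparison of two sequences, not of nintedanib with placebo. A reader who is not told this may take the placebo-randomised column as a placebo reference.

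The first is a contradiction between rules. The second is a display choice that lacks a label. What is at stake is correct attribution and correct reading of descriptive safety tables.

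**Working it through.** **1. The rules side by side**

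| Place | Unit | Counted under |
|---|---|---|
| Protocol 7.3 | safety parameters | treatment received |
| SAP 6.1 | patients, in safety analyses | treatment received |
| SAP 7.8.1, attribution sentence | adverse events | randomised treatment |
| SAP 7.8.1, pooled analysis | both periods together | randomised treatment |

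SAP 7.8.1 refers to 6.1 for the treatment definition, but 6.1 contains the opposite assignment rule, so the reference does not settle the conflict. Section 7.8.1 is also uneven within itself: its rule for collapsing occurrences into episodes asks whether treatment changed between onsets, which presupposes that treatment at onset is tracked.

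**2. Blinded-period table.** By Table 6.1: 1 the blinded safety period cannot run past first open-label intake. No open-label nintedanib time enters it. The two rules therefore differ here only for C1 or C2 switches. The documents give no expected number of these, so no size can be put on this part.

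**3. Pooled display.** Inputs: 233 placebo and 117 nintedanib patients (protocol 7.7); 12 and 40 weeks (protocol 3.1). The plan's own figure is reproduced: 52 − 12 = 40 weeks. The patient-weeks below assume that every patient completes treatment.

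- Placebo-randomised group, on placebo: 233 × 12 = 2,796 patient-weeks.
- Same group, on nintedanib: 233 × 40 = 9,320 patient-weeks.
- Nintedanib share of that group's time: 9,320 / (2,796 + 9,320) = 9,320 / 12,116 = 40/52 = 76.9%. Adding the 28-day residual period: 44/56 = 78.6%.
- All nintedanib time in the trial: 117 × 52 + 9,320 = 6,084 + 9,320 = 15,404 patient-weeks.
- Share of it shown in the placebo-randomised column: 9,320 / 15,404 = 60.5%.

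**4. What each correction reaches.** Changing the attribution sentence alone leaves the pooled display as it is, because the closing paragraph of 7.8.1 sets that grouping independently. A patient-level as-treated rule would not resolve it either, since every placebo patient who continues is treated with both. Either the event is attributed at onset or the column is named as a sequence.

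**The case against.** The strongest reply is that the attribution sentence is loose drafting and that the rest of the SAP contains the damage. Section 6.1 already separates blinded from open-label treatment and ends the blinded residual period at first open-label intake. The two periods are tabulated separately, so there is a 12-week randomised comparison and an open-label table in which the planned treatment is nintedanib for everyone. Related adverse events have their own table. No hypothesis is tested. Grouping 52 weeks by randomised arm is a legitimate grouping by sequence, and the pooled analysis is only an addition.

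Most of this stands. It also rules out some stronger readings that a reader might reach:

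- That the attribution sentence produces the pooled table. It does not; the pooled grouping is specified separately.
- That the pooled table would list nintedanib events under a column headed placebo. The documents do not give the heading. It may be fixed by sponsor standards or SAP sections that are not in the public text.
- That the plan conceals drug-related events. The separate-period tables show them, and no safety conclusion has to rest on the pooled table.
- That the pooling shrinks a treatment contrast by a stated number of points. Any such figure needs incidences that the documents do not give, and would set a 12-week difference against a 52-week one. The design has no 52-week placebo contrast to lose.

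What the reply does not remove is the conflict of rules. A programmer cannot follow both sentences for a C1 or C2 patient, and the reference to 6.1 does not say which prevails. Nor does it supply the missing sequence label.

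**Conclusion.** The concern holds as two limited points. First, the attribution sentence in SAP 7.8.1 contradicts SAP 6.1 and protocol 7.3, with no declared change of plan. Its practical effect is confined to patients with an actual treatment switch, whose number is unknown. Second, the pooled display puts up to 40 of 52 planned weeks (77%) of nintedanib time in the placebo-randomised group and does not require that this be stated. The 77% is the planned share for a patient who completes treatment; early discontinuation would change it.

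Apart from medication errors, the 12-week blinded comparison is clean. The adverse event analyses are descriptive, so no inferential result changes. This is a minor correction, worth making because it is cheap and because the rule as written is wrong.

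**What to change.** 1. In SAP 7.8.1, have treatment-emergent events attributed to the treatment actually being taken at onset, including its residual period, with the boundaries already set in SAP 6.1 and Table 6.1: 1. Apply the same rule to the repeat analysis with the 7-day window.
2. In the closing paragraph of 7.8.1, require the pooled columns to be labelled by sequence: placebo then nintedanib, and nintedanib throughout.
3. Optional: add an exposure-adjusted column for all time on nintedanib. Nothing in the documents requires it.

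Items 1 and 2 cost a few words in the SAP and changed table headings. They need no new data. Item 3 costs one more column.
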